Brief Summary	This is a prospective multicenter registry with an embedded open-label randomized clinical trial to determine the effects of standard of care treatment vs. standard of care plus AT-001 on cardiac structure and function and in-hospital survival in patients hospitalized for management of COVID-19 infection. Eligible subjects with COVID-19 infection will be identified at the time of hospital admission based on existing infection control surveillance protocols, and will have clinical data extracted from the electronic medical record to determine clinical characteristics associated with cardiac structure and function and in- hospital survival. A subset of patients with history of diabetes mellitus 		
Phase	Phase II		
Objectives	 To characterize serial measures cardiac structure and function and in-hospital survival in hospitalized patients with COVID-19 infection To develop predictive models of cardiac risk in hospitalized COVID- 19 infection patients To assess safety of treatment with AT-001 plus standard of care on in-hospital survival in patients with COVID-19 To characterize the effects of treatment with AT-001 plus standard of care on in-hospital mortality, progression of acute lung injury requiring mechanical ventilation, and serial measures of cardiac structure and function 		
Methodology	Prospective, open-label registry with embedded open-label study		

Endpoint	Primary Endpoint for Registry Study: Proportion of subjects with decreased left ventricular ejection fraction ≥10% from baseline at time of hospitalization Primary Endpoint for Embedded Clinical Trial: Safety of AT-001 Secondary Endpoints (for registry and clinical trial): • Change in left ventricular ejection fraction • Change in left ventricular ejection fraction • Change in left ventricular end-diastolic diameter • Change in left ventricular end-systolic diameter • Change in biomarkers of cardiac injury • Frequency of atrial fibrillation • Frequency of non-sustained ventricular tachycardia • Frequency of sustained ventricular tachycardia • Frequency of ventricular fibrillation • Frequency of sustained ventricular tachycardia • Frequency of ventricular fibrillation Proportion of subjects requiring mechanical ventilation • Proportion of subje			
Study Duration	One year			
Participant Duration	Up to 30 days after hospital discharge			
Duration of IP administration	1-14 days per treatment physician discretion			
Population	All subjects hospitalized with COVID-19 infection hospitalized will be enrolled in the registry; a subgroup meeting specific entry criteria listed below will be enrolled in the open-label interventional trial			
Study Sites	NYU Langone Tisch Hospital (registry and embedded clinical trial)NYU Langone Brooklyn Hospital (registry only)NYU Langone Winthrop Hospital (registry and embedded clinicaltrial)Bellevue Hospital Center (registry only)			
Number of participants	500 registry subjects enrolled at all sites 20 interventional trial subjects at NYU Tisch Hospital and NYU Winthrop			
Description of Study Agent/Procedure	AT-001 is an investigational novel Aldose Reductase Inhibitor (ARI) in Phase 2/3 development in the US, Canada and Europe for treatment of Diabetic Cardiomyopathy. The US IND# is 136043. A full Investigational Brochure is for the ongoing Diabetic Cardiomyopathy program is attached to this protocol.			
Reference Therapy	Standard of care			
Key Procedures	Data extraction from electronic medical record Administration of AT-001 1500 mg twice daily for up to 14 days			

	Registry Study
Statistical Analysis	 Multivariable logistic regression models and Cox Proportional Hazard models will be used to estimate the association between clinical variables at time of hospital admission and ICU admission with proportion of patients with decreased left ventricular ejection fraction ≥10% and secondary endpoints cardiac structure and function. Multivariable mixed models will be used to estimate the association between serial measures of cardiac structure and function and inhospital mortality.
	Interventional Study
	 Safety assessment of AT-001 based on reported adverse events Exploratory analyses with descriptive statistics to describe clinical outcomes in patients treated with AT-001 plus standard of care

Schematic of Study Design

1 Key Roles

Name	Role	Appointment	Department	Site
[name]	Principal Investigator	NYU Grossman SOM	Department of Medicine	NYU Tisch
[name]	Co-Investigator	NYU Grossman SOM	Department of Medicine	NYU Tisch
[name]	Co-Investigator	NYU Grossman SOM	Department of Medicine	NYU Tisch
[name]	Co-Investigator	NYU Grossman SOM	Department of Medicine	NYU Tisch
[name]	Co-Investigator	NYU Grossman SOM	Department of Medicine	NYU Tisch
[name]	Co-Investigator	NYU Grossman SOM	Department of Medicine	NYU Tisch
[name]	Co-Investigator	NYU Grossman SOM	Department of Medicine	NYU Winthrop

2 Background Information and Scientific Rationale

2.1 Background Information and Relevant Literature

An outbreak of viral pneumonia in Hubei province China in December 2019 led to the identification of a novel coronavirus (SARS-CoV-2, subsequently renamed as COVID-19) as the etiologic agent.^{1, 2} COVID-19 infection rapidly spread through China and then globally to all continents except Antarctica. Based on reported observations from the initial epidemic in China, hypertension and underlying cardiac diseases, as well as diabetes and treatment with immunosuppressants, may be associated with increased risk of death in patients with COVID-19. Like related coronaviruses, COVID-19 infects host cells via interaction with membrane-bound angiotensin converting enzyme-isoform 2 (ACE2) on respiratory epithelium. ACE2 is part of the renin-angiotensin-aldosterone (RAAS) neurohormonal pathway, a neuroendocrine, paracrine, and autocrine system that regulates cardiac structure and function, vasomotor tone, sodium metabolism, and blood pressure homeostasis. COVID-19 infection is also associated with activation of inflammatory cytokines that induce myocardial contractile dysfunction, myocyte cell injury, cardiac arrhythmias, and vascular endothelial cell and smooth cell dysfunction.

Initial reports from China in 41 patients indicated that severe COVID-19 infection in hospitalized patients is associated with approximately 10-20% risk of cardiac complications include increased biomarkers of myocardial injury, decreased left ventricular contractile function, cardiac arrhythmias, chest pain, hypotension, and fatal circulatory collapse.³ There are also reported anectodal cases of sudden cardiac arrest occurring in young patients recovering from COVID-19 induced acute respiratory failure.

The current study is being undertaken to create increase knowledge of the cardiovascular complications of COVID-19 infection at NYU Langone Health and Bellevue Hospital Center. A prospective registry is proposed to characterize the cardiovascular manifestations of COVID-19 CONFIDENTIAL

This material is the property of the NYU School of Medicine and Langone Medical Center. Do not disclose or use except as authorized in writing by the study sponsor

Interventional Template Version: 11 January 2019

infection in US patients. The prospective registry also provides a platform for execution of a clinical trial of an investigational agent for treatment of COVID-19 infection.

Aldose reductase (AR), the first and rate-limiting step in the polyol pathway, is activated by hyperglycemic and ischemic conditions. AR initiates this pathway by catalyzing the NADPH-dependent reduction of the aldehyde form of glucose to produce sorbitol as an intermediate. Sorbitol is then oxidized using NAD to form fructose, catalyzed by the enzyme sorbitol dehydrogenase. Excess intracellular sorbitol produced by AR accumulates in cells, resulting in osmotic damage and ultimately cell death (figure 1).^{4, 5}

[figure not shown]

Figure 1 Glucose Metabolism in the Polyol Pathway

Aldose Reductase plays a critical role in mediation of oxidative tissue damage in setting of inflammation induced by infection or ischemia.⁶ A potent Aldose Reductase Inhibitor (ARI) with a favorable safety profile may be an important tool for short-term use in the clinical setting to prevent lung inflammatory damage and cardiomyopathy in patients with COVID-19 infection.^{7, 8}

Aldose Reductase Inhibitors (ARIs), including the first-generation ARI zopolrestat, and the next generation ARI, AT-001 prevent oxidative-induced cardiac and lung injury in vivo and in vitro by preventing AR-induced downstream accumulation of reactive oxygen species and advanced glycation end-products. AT-001 has been shown to prevent oxidative damage to cardiomyocytes in oxidative-induced cardiomyopathies. AT-001 prevents ischemic/oxidative damage to cardiomyocytes in an ex-vivo system and decreases CK and other markers of cardiac damage In a Phase 1/2 clinical trial, AT-001 treatment in patients with Diabetic Cardiomyopathy decreased NTproBNP levels, a biomarker of cardiac stress or damage.

AT-001 demonstrates approximately 1,000-fold increased activity or potency vs. prior ARIs with excellent safety and tolerability profile. (see attach Investigator Brochure and Reference: Perfetti et al Overcoming the Safety Challenges of Aldose Reductase Inhibition: Development of AT-001 for Diabetic Cardiomyopathy; poster presented at WCIR Dec 2019;

https://www.appliedtherapeutics.com/wpcontent/uploads/2020/01/2019_WCIRDC_Poster_Final_1.pdf)

[figure not shown]
CONFIDENTIAL

This material is the property of the NYU School of Medicine and Langone Medical Center. Do not disclose or use except as authorized in writing by the study sponsor Interventional Template Version: 11 January 2019 This interventional trial is intended to allow open-label emergency use of AT-001 for COVID-19 infected patients experiencing acute cardiopulmonary sequelae of disease.

2.2 Name and Description of the Investigational Agent

AT-001 is a small molecule with a molecular weight of 421 g/mol. Its chemical structure is provided below.

Chemical Structure of AT-001

AT-001 drug product is provided as AT-001 powder in a capsule in a 500 mg strength, packaged in blister cards. There are no excipients used in the manufacture of AT-001 powder in capsule, and no materials of human or animal origin are present. The white, opaque capsule shells contain hypromellose and titanium dioxide. AT-001 is currently in Phase 2/3 development for Diabetic Cardiomyopathy under IND 136043. Based on pre-clinical and clinical data presented in the Investigator Brochure, a dose of 1,500mg BID (3 X 500mg capsules twice daily) will be used.

AT-001 is an inhibitor of aldose reductase (AR), the first and rate-controlling enzyme of the polyol pathway which converts glucose to sorbitol and then to fructose. Hyperactivation of this pathway in patients with diabetes is thought to play a critical role in the pathogenesis of diabetic complications, including damage to peripheral nerves and blood vessels. Excess intracellular sorbitol produced by AR accumulates in cells, resulting in osmotic damage and ultimately cell death (Miki 2013). This pathological effect of excess sorbitol in cardiac cells can be seen in ventricular myocardial biopsies from diabetic patients which show significantly higher necrotic cardiomyocytes compared to biopsies from non-diabetic patients (Frustaci 2000).

In vitro assays demonstrate that AT-001 binds to AR with high affinity and specificity, and with no evidence of off-target effects. In in vivo animal studies, AT-001 normalized sorbitol levels in diabetic rats, prevented cardiac ischemic injury in diabetic mice, prevented acute cardiac ischemic injury in non-diabetic rats, and treated acute cardiac ischemic injury in non-diabetic rats.

2.2.1 Preclinical Data

A comprehensive program to evaluate the preclinical profile of AT-001 has been conducted to support the clinical development program. In vivo Good Laboratory Practice (GLP) safety pharmacology studies showed no effect of AT-001 on gross behavioral, physiological, or neurological function in rats (Irwin Test), and no cardiovascular or respiratory effects in dogs at doses up to 2000 mg/kg/day, the highest dose studied. The AT-001 oral toxicology program to date consists of two single-dose studies in rats, one single-dose study in dogs, a dose range finding study in rats, a dose range finding study in dogs, two definitive 28-day GLP studies (rats, dogs); and two chronic GLP toxicity studies conducted in rats (26 weeks) and dogs (39 weeks). In vitro and in vivo genotoxicity testing has been performed. Doses up to 2000 mg/kg/day have

been orally administered to rats and dogs for up to 39 weeks. In the single-dose studies, the MTD was considered to be 2000 mg/kg/day, since there were no findings in these studies. In the 28-day toxicology studies, the no adverse effect level (NOAEL) was determined to be 2000 mg/kg/day in both rats and dogs. Four reproductive studies of the effects of AT-001 have been conducted: 2 studies in rats (GLP) and 2 studies in rabbits (one non-GLP, one GLP). Based on these findings, the NOAEL for maternal and embryo/fetal developmental toxicity was 1000 mg/kg/day (the highest dosage level tested) in rats and 200 mg/kg/day in rabbits. AT-001 was shown to be negative for mutagenic activity in the reverse mutation assay, negative in the in vitro micronucleus assay, and negative in the in vivo micronucleus assay.

2.2.2 Clinical Data to Date

To date, one clinical study (AT-001.1001) has been conducted with AT-001. Full details are provided in the attached Investigator Brochure.

StudyAT-001-1001, the first in human study of AT-001, was a Phase 1-2, three-part, randomized, placebo-controlled study designed to assess the safety, tolerability, PK, and PD (effect on sorbitol) of AT-001 in adults with Type 2 Diabetes Mellitus (T2DM). Since AR converts glucose to sorbitol, and AR activity is elevated in diabetic patients, sorbitol normalization was examined as a PD biomarker of target engagement. The study had 3 parts: single ascending dose (SAD) (Part A), 7-day multiple ascending dose (MAD) (Part B), and a 28-day MAD extension part (Part C). A thorough safety review of each dose cohort was conducted prior to escalation to the next higher dose.

All doses and dosing regimens were well-tolerated with no safety issues identified. There were no serious adverse events (SAEs) considered treatment-related and no AEs causing discontinuation of study treatment. No clinically relevant changes in vital signs, ECG or clinical safety laboratory values were noted. AT-001 did not cause an increase in glucose levels and was not associated with adverse interactions with any concomitant diabetes medications used by patients during the study.

Mean AT-001 Tmax was between 1.5 to 3 hours, and mean half-life ranged between 1.2 to 3.4 hours across all SAD and MAD cohorts. The maximal and systemic exposure in terms of Cmax and AUC0-inf appear to increase with increasing dose in a dose proportional manner in SAD cohorts, as well as in MAD cohorts on Days 1, Day 7, and day 28. AT-001 did not accumulate in plasma following administration of daily doses for up to 28 days.

No clinical drug interaction studies have been conducted with AT-001 to date. The potential of AT-001 to inhibit the catalytic activities of key CYP isoforms was evaluated in an in vitro metabolism study using recombinant human CYP isoforms, while its potential to induce the catalytic activities of key CYP isoforms was evaluated in an ex vivo metabolism study using human hepatocytes. AT-001 over the concentration range tested (0.00545 to 50.0 μ M) did not significantly inhibit human CYP450 isozymes 1A2, 2B6, 2C8, 2C9, 2C19, 2D6, and 3A4 (midazolam and testosterone substrates). The induction of human CYP1A2, 2B6, and 3A4 by AT-001 at the highest concentration tested (100 μ M), observed in one of the three lots of hepatocytes, was lower than that with the control inducers which produced effects in all lots of hepatocytes.

2.2.3 Dose Rationale (if applicable)

The 1500 mg twice daily dose is based on safety observations from the 28-day multiple ascending dose extension study.

2.3 Rationale

COVID-19 and previous coronaviruses associated with acute respiratory syndrome have high mortality rates, primarily attributable to respiratory failure and a substantial minority with cardiovascular complications. The proposed study will provide novel data in US patients to enhance cardiovascular risk prediction and identify potential novel therapies for therapy.

2.4 Potential Risks & Benefits

2.4.1 Known Potential Risks

In subjects enrolled in the prospective registry, the only risk is potential breach of confidentiality.

In subjects enrolled in the interventional trial, additional risk is associated with investigational agent. In the completed first in human study (Study AT-001.1001) AT-001 was generally well tolerated with no safety issues identified. There were no SAEs considered treatment-related and no AEs causing discontinuation of study treatment. No clinically relevant changes in vital signs, ECG or clinical safety laboratory values were noted.

Potential risks of AT-001 based on non-clinical data and previous experience with other aldose reductase inhibitors include:

- Acute hypersensitivity reactions
- Hepatic toxicity, including fatal hepatic necrosis
- Renal toxicity: Nephrolithiasis (calculi and pelvic dilation suggestive of an obstructive mechanism leading to development of pyelonephritis were reported in female rats in a 6-month chronic toxicology study. These renal findings were not reproduced in dogs in a 9-month chronic toxicology study)
- Gastrointestinal events, including nausea, vomiting, diarrhea, flatulence, abdominal pain
- Ocular effects (two cases of non-adverse, reversible multifocal pinpoint corneal opacities in a 28day toxicology study in dogs, which was not reproduced in a 9- month chronic toxicology study)
- Hypotension and dizziness
- Skin rash/eczema
- Decreases in hemoglobin, erythrocyte count, and lymphocyte count
- Reduction in total protein in blood

The incidence of these side effects for short-term exposure to AT-001 in COVID-19 patients is unknown. We anticipate that patients with COVID-19 infection will receive concomitant treatments including off-label use of FDA-approved drugs, anti-viral therapy with remdesivir under expanded access or emergency use access, and treatment with hydroxychloroquine, convalescent sera, and/or IL-6 inhibitors within the context of clinical trials. Based on knowledge of the pathophysiology of COVID-19 infection and the pharmacology of AT-001, we do not anticipate that these concomitant medications will increase risk associated with AT-001. Patients with COVID-19 infection are known to be a high risk of complications including

multisystem organ failure (liver, kidney, heart, lung, hematological system, nervous system with associated laboratory abnormalities) and septic shock (hypotension with metabolic abnormalities). We will collect daily clinical information to monitor evidence of organ dysfunction and septic shock in the electronic CRF. We will identify potential AE related to study drug based upon temporal relationship with study drug administration, AE in the above list of potential AE associated with aldose reductase inhibition, or suspicion that the magnitude and/or duration of organ dysfunction and associated laboratory abnormalities is different from that expected due to COVID-19 infection alone. If treatment related AE are identified, the study drug may be discontinued per the discretion of the PI, Sponsor, and treating physician.

2.4.2 Known Potential Benefits

There is no direct benefit to subjects enrolled in the prospective registry.

Based on its known mechanism of action and observations in the first in human study, there is possible benefit to subjects who receive AT-001 in the interventional study.

3 Objectives and Purpose

3.1 Primary Objective

- Registry Study: To characterize serial measures cardiac structure and function and in-hospital survival in hospitalized patients with COVID-19 infection
- Interventional Trial: To characterize safety of AT-001 in hospitalized patients with COVID-19 infection

3.2 Secondary Objectives (if applicable)

- To develop predictive models of cardiac risk in hospitalized COVID-19 infection patients
- To assess safety of treatment with AT-001 plus standard of care on in-hospital survival in patients with COVID-19
- To characterize the effects of treatment with AT-001 plus standard of care on in-hospital mortality, progression of acute lung injury requiring mechanical ventilation, and serial measures of cardiac structure and function

4 Study Design and Endpoints

4.1 Description of Study Design

The proposed study is a prospective registry of patients hospitalized with COVID-19 infections at participating sites (NYU Tisch, NYU Brooklyn, NYU Winthrop, Bellevue Hospital Center). Clinical data related to the COVID-19 infection will be extracted from the electronic medical record as described below in patients who meet study entry criteria. To maintain confidentiality, all subjects will be assigned a unique study identifier number. De-identified data will be recorded in an electronic database (REDCap).

A subset of patients enrolled in the registry study may be eligible to participate in an open-label interventional trial of AT-001. For the substudy, informed consent will be obtained at the time of study entry, and clinical data will be extracted from the medical record using the same protocol

as the registry study. Additional safety and tolerability data will be collected for patients participating in the interventional trial.

4.2 Study Endpoints

4.2.1 Primary Study Endpoints

Primary Endpoint for Registry Study: Proportion of subjects with decreased left ventricular ejection fraction $\geq 10\%$ from baseline at time of hospitalization

Primary Endpoint for Embedded Clinical Trial: Safety of AT-001 based on adverse events reporting

4.2.2 Secondary Endpoints

Secondary Endpoints (for registry and clinical trial):

- Change in left ventricular ejection fraction
- Change in left ventricular end-diastolic diameter
- Change in left ventricular end-systolic diameter
- Change in biomarkers of cardiac injury
- Frequency of atrial fibrillation
- Frequency of heart block
- Frequency of non-sustained ventricular tachycardia
- Frequency of sustained ventricular tachycardia
- Frequency of ventricular fibrillation

Secondary Endpoints (for clinical trial):

- Proportion of subjects requiring mechanical ventilation
- Proportion of subjects with decrease in left ventricular ejection fraction ≥10% from baseline at time of hospitalization

5 Study Enrollment and Withdrawal

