5.2 Exclusion Criteria

Registry Study: An individual who meets any of the following criteria will be excluded from participation in the registry study:

- 1. Persons who have opted out of research participation at NYU
- 2. Pregnancy

Interventional study: An individual who meets any of the following criteria will be excluded from participation in the interventional study:

- 1. Persons who have opted out of research participation at NYU
- 2. Pregnancy
- 3. Women of childbearing potential
- 4. Breast-feeding women
- 5. Participation in another FDA-regulated investigational drug placebo-controlled clinical trial within previous 30 days
- 6. Hospital length of stay at time of study entry >14 days
- 7. Inability to comply with oral or nasogastric tube administration of study drug

Co-enrollment in other interventional studies in the COVID-19 population will be permitted if in the judgement of the PI and Sponsor, there is no anticipated increase in risk of exposure to AT-001 based on the known pathophysiology of COVID-19 infection and pharmacology of AT-001, and co-enrollment is permitted in the other protocol(s). Co-enrollment will be tracked at reported to the IRB and Sponsor.

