7.3.1 Enrollment/Baseline

Enrollment/Baseline Visit (Visit 1, Day 0)

- Obtain informed consent for potential participant (or their LAR) verified by signature on study informed consent form.
- Verify inclusion/exclusion criteria.
- See electronic case report form. These data will be collected at baseline.
- Start study drug administration
- Safety monitoring

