10.3 Analysis Datasets

The registry dataset consists of all subjects with any entered data. The interventional safety data set will be all subjects who received at least one dose of AT-001

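### The trial's secondary LVEF endpoint is anchored at hospital admission rather than at the first AT-001 dose, and the ventilation endpoint does not separate new from existing cases

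*Combined protocol and SAP*

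**What the plan says.** Section 4.2.2 lists two endpoints for the clinical trial only: "Proportion of subjects requiring mechanical ventilation" and "Proportion of subjects with decrease in left ventricular ejection fraction ≥10% from baseline at time of hospitalization". The LVEF wording closely follows the registry's primary endpoint in Section 4.2.1 ("Primary Endpoint for Registry Study: Proportion of subjects with decreased left ventricular ejection fraction" and so on), which also refers back to hospitalization.

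The trial has a different starting point. Section 5.2 excludes a patient only for "Hospital length of stay at time of study entry >14 days", so a stay of up to and including 14 days is allowed at entry. Section 7.3.1 names the "Enrollment/Baseline Visit (Visit 1, Day 0" and lists under it "Start study drug administration".

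Section 3.2 includes among its objectives the effect of AT-001 on "progression of acute lung injury requiring mechanical ventilation" and on serial cardiac measures. Section 10.3 gives one analysis set for the trial: "The interventional safety data set will be all subjects who received at least one dose of AT-001". Section 10.2 says that secondary endpoints are summarized descriptively, without tests.

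**The concern.** An admission baseline suits a registry that follows patients from admission. Carried over to the trial, it opens the observation period up to 14 days before the drug is given. The resulting proportion mixes what happened before treatment with what happened after it, yet Section 3.2 intends it to characterize the effects of AT-001.

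The ventilation endpoint has a related gap. It states no time origin, no at-risk group and no period. The objective describes a new event, while the only analysis set is everyone dosed, and that set can include patients already ventilated at Day 0. Section 8.3 separates a condition present at screening from later deterioration for adverse events; Section 4.2.2 makes no such separation.

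What is at stake is how two descriptive figures can be read. Type I error, power and the primary safety endpoint are not involved.

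**Working it through.** The plan gives no figure to reproduce: 20 is a convenience sample (Section 10.5), with no event rate for either endpoint.

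**LVEF: what the text implies**

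1. Reference point: hospitalization (4.2.2).
2. Latest entry: a stay of 14 days (5.2).
3. First dose: the trial's Day 0 visit (7.3.1).
4. The gap between reference point and first dose is therefore 0 to 14 days. A fall of the required size within the gap meets the endpoint. The trial has its own baseline visit, but 4.2.2 names hospitalization, so 7.3.1 does not repair the wording.

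**LVEF: size per patient**

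Let n be the patients with evaluable pairs, x those counted as written, and d those among x whose fall was wholly before the first dose. With n held fixed, the figure as written is x/n and the re-anchored figure is (x − d)/n, a difference of d/n. For d = 1:

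- n = 20: 1/20 = 5.0 points
- n = 15 (assumed): 1/15 = 6.7 points
- n = 10 (assumed): 1/10 = 10.0 points

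The difference arises only if a patient has an LVEF recorded after admission and before the first dose. Otherwise the admission value is also the last pre-dose value and d/n = 0. LVEF comes from the medical record (7.1.1), and the Schedule of Events lists no echocardiogram, so d cannot be estimated.

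**Ventilation: two readings of one sentence**

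Let k of 20 patients be ventilated at Day 0 and m be new cases after the first dose.

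- Ever ventilated, all dosed: (k + m)/20
- New cases among those at risk: m/(20 − k)
- Difference: k(20 − k − m) / [20(20 − k)]

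At k = 0 the readings agree. With assumed values m = 3 and k = 5 they give 8/20 = 40% and 3/15 = 20%; by the formula, 5 × 12 / (20 × 15) = 0.20. This shows only that the sentence can yield two different numbers. The documents give neither k nor m.

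**Can k exceed zero?** No exclusion in 5.2 covers ventilated patients. The close of Section 2.1 says the trial is meant for patients with acute cardiopulmonary sequelae, Section 5.4 has the intensivist identify candidates, and Section 6.1.6 provides for nasogastric dosing. Section 5.4.1 also finds patients on COVID-19 floors, and Section 5.1 is silent on current cardiac or pulmonary involvement: it neither requires nor excludes it. Ventilation at entry is plausible, but its frequency is unknown.

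**The case against.** The strongest reply is that little depends on this. The endpoints are exploratory and descriptive in about 20 patients (10.2, 10.4.2), and Section 10 plans no comparison with a control group. With no scheduled echocardiogram, few patients may have two LVEF values before the first dose, and then the anchor makes no difference. Section 7.3 collects trial data daily during dosing, which suggests a post-dose intent. The eCRF, an attachment not seen here, may let the analyst separate pre-dose from post-dose status.

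Most of this stands, and it limits the weight of the point. It does not remove it. Section 7.3 governs data collection rather than endpoint definition, and Section 4.1 says that trial data are extracted in the same way as registry data. A descriptive proportion still needs a defined numerator and denominator.

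Three stronger readings are tempting and are not supported:

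- *That the bias is large.* One might apply the 10–20% risk of cardiac complications in Section 2.1, or an assumed share ventilated at entry. The former covers all cardiac complications in severe cases and gives no timing of LVEF falls; the latter appears nowhere.
- *That the ventilation endpoint is wrongly defined.* It is incompletely defined, and a post-dose reading remains open.
- *That re-anchoring would show the drug's effect.* It removes pre-dose events, but without a planned comparison it does not by itself isolate an effect of AT-001.

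**Conclusion.** The point holds in a limited form. As written, the trial's LVEF endpoint counts a fall that was complete before the first dose. This follows from Sections 4.2.2, 5.2 and 7.3.1 without any assumption. Its size is 1/n per affected patient, and zero where the admission LVEF is the last one before dosing; the number affected cannot be derived. The ventilation endpoint is under-specified relative to the objective in Section 3.2, and its two readings differ in practice if some, but not all, patients are already ventilated at Day 0 and not every patient at risk becomes a new case.

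Severity is minor, but the text should be corrected. Confidence is medium, because routine LVEF timing and the eCRF content are unknown.

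**What to change.** Amend Section 4.2.2 for the clinical trial only:

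1. **LVEF.** Define baseline as the last value before the first AT-001 dose and count only falls observed after that dose. Report the date of the baseline value and the number of patients with evaluable pairs. Keep the admission-anchored figure alongside for consistency with the registry.
2. **Ventilation.** Report new mechanical ventilation after the first dose among patients not ventilated at Day 0, over one stated period. List Day 0 ventilation status separately. Show in-hospital deaths and discharges in that period, and note that in-hospital follow-up ends at discharge.

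One feasible period is 14 days from the first dose. Entry after a stay of at most 14 days gives 14 + 14 = 28 days, within the 30 hospital days of registry collection in Section 7.3, provided that trial patients stay in the registry as Section 4.1 implies. Relying on collection during dosing alone would give periods of 1 to 14 days, depending on the patient.

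The cost is a text change; no procedure is added. There are three downsides. The ventilation denominator shrinks: in the assumed example, 3/15 has an exact 95% interval of 4.3% to 48.1%. Some patients may have no pre-dose LVEF. The trial and registry definitions of the LVEF fall will differ, which is why both figures are kept. Check that the eCRF records the LVEF date and the start of ventilation.
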